Endpoints	
The primary outcome is the proportion of hearts transplanted (the number of hearts transplanted divided by the total number of potential donors).
 
The safety outcome is proportion of hearts transplanted that maintain graft function at 30-days and 1-year.
 
Secondary outcomes will include: 1) time from randomization to weaning off vasopressors: defined as being off all vasoactive agents (except for vasopressin); 2) proportion weaned off vasopressors by 12-hours (same criteria as #1); 3) time achieving hemodynamic stability adequate to order first echocardiograph; 4) left ventricular ejection fraction measured on first donor echocardiography; 5) total number of organs transplanted

Population	We plan on enrolling 800 brain dead organ donors with authorization for donation and research in order to have 752 evaluable subjects who receive the study drug or placebo
Phase	Three
Number of Sites	Est. 14 OPOs, 1 coordinating site for human (recipient) data
Study Duration	18-24 months

Abbreviations

AOPO, Association of Organ Procurement Organizations

BD, brain dead

DSMC, data and safety monitoring committee

LVEF, left ventricular ejection fraction

OPO, organ procurement organization

ODRC, Organ Donation Research Council

OPTN, Organ Procurement and Transplant Network

SRTR, Scientific Registry of Transplant Recipients

T4, thyroxine

TTE, transthoracic echocardiography

UNOS, United Network for Organ Sharing

Administrative information

Title {1}	A Multicenter Randomized Placebo-Controlled Trial of Intravenous Thyroxine for Heart-Eligible Brain Dead Organ Donors
Trial registration {2a and 2b}.	Clinicaltrials.gov NCT04415658. Registered June 4, 2020. https://clinicaltrials.gov/ct2/show/NCT04415658
Protocol version {3}	3.0
Funding {4}	None (internal administrative support provided by Mid-America Transplant)
Author details {5a}	[name], Washington University in St. Louis School of Medicine [name], Mid-America Transplant
Name and contact information for the trial sponsor {5b}	Mid-America Transplant [name]
Role of sponsor {5c}	Mid-America Transplant will not have any role in the design or analysis of the trial data. They will not have any role in the writing of the manuscript or the decision to submit the report for publication.

Introduction

Background and rationale {6a}

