Primary: Intravenous thyroxine (T4) will increase the proportion of hearts transplanted when given early after brain death to heart-eligible hemodynamically unstable potential organ donors

Safety: Hearts transplanted from donors receiving T4 will have non-inferior graft survival to those from the placebo group at 30-days

Secondary: T4 will reduce time to wean off vasopressors and improve cardiac ejection fraction

Trial design {8}

Randomized in parallel groups to intravenous thyroxine or saline placebo in 1:1 ratio

Randomization will be in blocks, stratified by OPO site, allowing each site to serve as its own control (given heterogeneity in donor management protocols between OPOs)

Administration of study drug or placebo will not be blinded

Methods: Participants, interventions and outcomes

Study setting {9}

This study will be performed under the auspices of various Organ Procurement Organizations (OPOs) across the country (list of active sites available on clinicaltrials.gov). Participants will be patients already declared dead by neurologic criteria (i.e. brain dead) and who have provided authorization (first-person or by living surrogates) for both organ donation and for research. They may be physically located either/both in the hospitals in which they were declared and/or at an independent recovery/donor management facility of the OPO. The donor component has been deemed not to involve human subjects research and participating hospitals and OPOs are therefore not engaged in human subjects' research. The coordinating site (Washington University in St. Louis) will be the research site responsible for collecting recipient outcome data. A waiver of consent has been obtained for de-identified collection of this human recipient data.

Eligibility criteria {10}

Inclusion Criteria:

1. Declared dead by neurologic criteria
2. Provided authorization for organ donation and for research
3. Donor age of 14-55 years (inclusive) and weight \geq 45 kg (100 lbs)
4. On one or more vasopressor and/or inotropes (not including vasopressin)

Exclusion Criteria:

1. Brain death declared $>$ 24 hours prior
2. Known CAD or MI (by history, EKG, or previous cardiac cath)*
3. Significant valvular heart disease (by history of echo)*
4. Prior sternotomy or cardiac surgery*
5. Donor at VA hospital
6. Received intravenous or oral thyroid hormone in the past month
7. Known HIV+ status

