8. Additional outcomes routinely collected from heart transplant recipients will also be aggregated and analyzed, including need for post-transplant mechanical circulatory support and other measures of primary graft dysfunction

Safety endpoints:

The following adverse events will be prospectively collected on all study donors. All events deemed either related or potentially related to the study drug infusion will be reviewed by the site coordinator. Any serious related events (defined as hemodynamic instability leading to cardiac arrest or donor loss prior to organ recovery) will be forwarded to the DSMC for additional review:

1. Severe hypertension (systolic BP > 200 mm Hg)
2. Tachycardia (HR > 150 and increased more than 20 over baseline)
3. New/worsened tachyarrhythmia (SVT, Atrial fibrillation, Ventricular tachycardia or fibrillation)
4. Cardiac arrest or any donor loss prior to the OR
5. Fever – new, above 102 degrees Celsius
6. New skin rash

Participant timeline {13}

Sample size {14}

The proportion of potential heart donors who were able to provide a heart for transplantation in our pilot studies was between 30-60% (12, 14), a rate concordant with the recent literature (23). Proposed effect sizes of thyroid hormone treatment have ranged as high as an absolute increase of 20% or more in proportion of hearts transplanted in non-randomized studies (24); a large retrospective analysis of UNOS data found that those who received thyroid hormone (57% of 40,124 donors) had more hearts transplanted (7). The increase was from 25.8% without treatment to 35% with thyroid hormone (among all donors, not only those who were strictly heart-eligible, as required in this study). Based on our pilot data and this literature, we propose an absolute treatment effect size of 10% as the threshold for this study. In order to detect an increase in the proportion of hearts transplanted from 35% to 45%, we will need 752 total donors (376 per group), assuming 80% power and a one-sided alpha of 0.025. Because we expect some loss of donors after enrollment (e.g., clinical issues that interrupt adherence to the protocol), we will enroll a total of 800 donors (400 in each study group).

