For our safety analysis in recipients of donor hearts, we have calculated a sample size necessary to demonstrate non-inferiority in graft survival. Based on recent data provided by SRTR, the expected 30-day graft survival after heart transplantation is 96%. We will test for a decrease of no greater than 6% in graft survival (i.e. from 96% to 90%; see *Statistical Methods* for a full explanation of assumptions and testing). With one-sided alpha of 0.025, we would need 336 recipients (168 per group) to have 80% power to exclude such a difference. Therefore, based on our sample size of 800 donors and an expectation that overall at least 40% of donor hearts will be transplanted, we expect a minimum of 320 recipients for this analysis; this sample size will provide a power of 78% for non-inferiority. It is likely that more than 40% of hearts will be transplanted; in fact, we saw in excess of 50% of hearts transplanted in our pilot data. Therefore we expect to have more than the required number of recipients to achieve 80% power. This sample size of recipients would also provide 80% power to demonstrate non-inferiority at the one-year survival endpoint.

Recruitment {15}

There are between 50 and 100 heart-eligible organ donors per year managed at most OPOs (of variable sizes) around the country. Therefore we are recruiting at least 10 OPO sites (est. 50 participants per OPO per year) in order to complete recruitment of adequate donors (n=800) within a 18-month study period.

Assignment of interventions: allocation

Sequence generation {16a}

A random sequence of 1s and 0s will be computer-generated by the central coordinating site in blocks of 30 for each participating OPO site (i.e. stratified by site). A web-accessible randomization sheet will be provided to each site with three such blocks (i.e. randomization key for 90 potential subjects).

Concealment mechanism {16b}

Only once eligibility has been confirmed will the on-site organ procurement coordinator will login to the website with the randomization list and determine (using the next available row) to which group the donor has been assigned. The coordinator will enter the UNOS# of the donor on the randomization form, as well as

the time and date of enrollment in the study before communicating the study assignment to OPO staff. The site study coordinator will review the randomization log to ensure that all eligible donors are being randomized and that sequential randomization rows are utilized.

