We will present descriptive statistics for demographic and clinical variables, including by study group, but will not perform statistical comparisons of differences between study groups for baseline variables that should be balanced by randomization. We will first evaluate the primary outcome, the proportion of hearts transplanted, presenting the absolute and relative differences between the study groups, along with 97.5% one-sided confidence intervals. For our primary analysis, we will test the association between treatment and proportion of hearts transplanted, using a one-sided chi-square test at significant level of 0.025. Then we will proceed to a multivariate model that adjusts for potentially confounding variables and random site effect. The SRTR registry has developed comprehensive organ-specific risk-adjustment models (25). Older age and blood group are consistently the most important variables impacting whether hearts are transplanted. For this reason, we will include age and blood type as relevant pre-specified covariates. Since randomization was stratified by site, and imbalance in sample size across sites are expected, we will also include site as a random effects in our multivariate model. This will provide subject-specific measures of treatment effect, in terms of a conditional effect size and adjusted odds ratio (with 97.5% one bound confidence interval).

Given that a systematic assessment of non-randomized studies using T4 for heart donors has suggested an improved rate of hearts transplanted, while prior small randomized studies have suggested no effect (i.e. no studies suggesting that T4 therapy results in worse heart outcomes) (10), we have selected a superiority design as most appropriate for our primary outcome. We are seeking to ascertain whether the addition of T4 infusion to standard donor care results in more hearts transplanted. Therefore, our null hypothesis is that T4 treatment results in an equal or lower rate of hearts transplanted, meaning our alternate hypothesis is that T4 treatment is superior to no treatment. If the null hypothesis were not excluded, there would be no rationale to use T4 in addition to standard donor management and no benefit to focusing on a two-sided test evaluating whether it was worse than placebo. Therefore statistical tests will be one-tailed at a stringent significance

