Our plans for analyzing the secondary outcomes are as follows: for outcome measures that are time-to-event variables such as time to get off vasopressors and time to order first echo, we will perform Cox regression model to assess Hazard Ratio (95% confidence interval) between groups. We will calculate the vasopressor-inotrope score, VIS (27) as: $VIS = \text{dopamine dose } (\mu\text{g/kg/min}) + \text{dobutamine dose } (\mu\text{g/kg/min}) + 100 \times \text{epinephrine dose } (\mu\text{g/kg/min}) + 100 \times \text{norepinephrine dose } (\mu\text{g/kg/min}) + 10 \times \text{milrinone dose } (\mu\text{g/kg/min}) + 100 \times \text{phenylephrine dose } (\mu\text{g/kg/min}) + 10,000 \times \text{vasopressin dose } (\text{U/kg/min} - \text{only for doses } > 1 \text{ U/hour})$. We will compare the decrease in VIS from start of thyroid hormone or saline infusion until 12-hours (end of study infusion), using analysis of covariate method with predictor variables that include the baseline score and the treatment groups and adjusting for site effect. Cardiac ejection fraction will be evaluated using a linear mixed model adjusting for random site effect. If normality assumption is violated, data transformation will be performed. Count data regarding thoracic and total organs transplanted will be compared using Generalized Estimating Equations, with study group as the independent variable and expected organs transplanted as a covariate. All secondary outcome analyses will be two-tailed test at a significance level of 0.05.

Interim analyses {21b}

The DSMC statistician will perform one interim analysis when 376 donors have been enrolled with evaluable data. The trial may be terminated early if, based on the judgement of the DSMC, the interim findings

demonstrate either superiority or clear inferiority of T4 treatment compared to placebo (at a threshold of 0.01). The trial may also be terminated if there is inferiority of graft outcomes in either group, observed at 30-days in those hearts transplanted and observed for this period. The DSMC will provide recommendations to the study PIs, who will make final decisions about whether to stop or continue the trial.

Methods for additional analyses (e.g. subgroup analyses) {20b}

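### The organ-count GEE omits the OPO, on which randomization is stratified, and names no cluster; adding OPO as a fixed effect is a one-sentence improvement to a secondary analysis

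*Combined protocol and SAP*

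**What the plan says.** Under Statistical methods {20a}, the counts of thoracic and of total organs transplanted "will be compared using Generalized Estimating Equations, with study group as the independent variable and expected organs transplanted as a covariate". The sentence names two model terms. It does not give the cluster unit, link, working correlation, variance estimator or reference distribution. On the error rate: "All secondary outcome analyses will be two-tailed test at a significance level of 0.05".

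Site is treated differently elsewhere:

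- Trial design {8}: "Randomization will be in blocks, stratified by OPO site". Sequence generation {16a} sets blocks of 30 within each OPO.
- Statistical methods {20a} puts a random site effect in the adjusted model for the primary outcome, and gives the reason: "Since randomization was stratified by site, and imbalance in sample size across sites are expected".
- In the same section, the vasopressor-inotrope score analysis adjusts for site, and the ejection-fraction model has a random site effect.
- Protocol Summary, Number of Sites: "Est. 14 OPOs, 1 coordinating site for human (recipient) data". Recruitment {15} gives a floor: "we are recruiting at least 10 OPO sites".
- Sample size {14}: "we will enroll a total of 800 donors (400 in each study group").

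The Protocol Amendment History explains the move to GEE only as more flexible than fixing a Poisson model in advance; it does not mention clustering. Another entry there says site enters the models for primary and secondary outcomes. I use that log only as evidence of intent.

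**The concern.** A GEE needs a cluster unit. Each donor contributes one value per count outcome, so the unit is either the donor or the OPO, and the two behave differently.

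With the donor as cluster and no site term, the standard error includes between-OPO variation that stratified randomization has already removed from the treatment comparison. The test is then too cautious, and precision that the design has paid for is lost.

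With the OPO as cluster, the ordinary sandwich variance rests on about 14 independent units. It is biased downwards with so few, and a normal reference ignores its own sampling error.

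Total organs transplanted is a listed secondary outcome. In the placebo-comparison pilot described under Background and rationale {6a}, organs per donor was the result that reached significance (median 5 vs 3, p=0.009), whereas hearts transplanted (p=0.14) and ejection fraction (p=0.24) did not. A positive count result here would draw attention. The trial is unblinded, so the choice of cluster should not be left until the data are in.

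**Working it through.** **The plan's own figures.** The plan gives no power or error-rate calculation for the count outcomes, only the nominal two-sided 0.05. The trial size does reproduce. For 35% vs 45%, one-sided alpha 0.025 and 80% power, n per group = [1.960√(2×0.40×0.60) + 0.842√(0.35×0.65 + 0.45×0.55)]² / 0.10² = (1.358 + 0.580)² / 0.01 ≈ 376, or 752 in total.

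**Inputs.** From the protocol: 800 donors, 1:1, blocks of 30 within OPO, about 14 OPOs (at least 10), unequal site sizes expected, two-sided 0.05. Assumed, because the documents give no values: the mean and distribution of organs per donor, the between-site SD, and the degree of imbalance in site size.

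**Donor as cluster, no OPO term, by hand.** Assume Poisson counts with mean 3.5 and between-site SD s on the log scale. Between-site variance is about (3.5s)², against a within-site variance of 3.5. The reported standard error is too large by r = √[(3.5 + (3.5s)²)/3.5], so the effective critical value is 1.96r. For a test with 85% power when site is in the model, power falls to Φ(1.960 + 1.036 − 1.96r).

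| s | (3.5s)² | r | 1.96r | type I error | power |
|---|---|---|---|---|---|
| 0.15 | 0.276 | 1.039 | 2.036 | 4.2% | 83% |
| 0.30 | 1.103 | 1.147 | 2.248 | 2.5% | 77% |

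Simulation with 14 sites and 800 donors agreed: type I error 2.4-5.1%, and power 82% vs 85% at SD 0.15 and 76% vs 85% at SD 0.30. That is a loss of 3 and 9 points.

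**OPO as cluster, uncorrected sandwich, normal reference, by hand.** With G equal clusters the sandwich variance is low by about (G−1)/G, and the corrected statistic is roughly t on G−1 df. The true rejection rate is therefore about 2·P(t on G−1 df > 1.96√[(G−1)/G]):

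- G = 14: 2·P(t13 > 1.889) = 8.1%
- G = 10: 2·P(t9 > 1.859) = 9.6%

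This needs no assumption about site variation; unequal sites tend to make it worse.

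**Simulation under the null.** Log-link GEE with Poisson variance, 800 donors, 14 OPOs, blocks of 30, 0-8 organs per donor, expected organs about 3.5 (SD 1), independence working correlation, 2,500 runs per row (Monte Carlo SE about 0.6 points). Unequal site sizes were drawn from Dirichlet(2) and very unequal ones from Dirichlet(1). Rejection rates in %:

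| Site sizes | Site SD (logit) | Donor cluster, no OPO | OPO cluster, normal | OPO cluster, t(13) | OPO cluster, Mancl-DeRouen, t(13) |
|---|---|---|---|---|---|
| equal | 0 | 5.4 | 8.3 | 5.7 | 4.4 |
| equal | 0.25 | 5.2 | 9.3 | 6.2 | 4.8 |
| equal | 0.5 | 3.4 | 7.5 | 5.0 | 4.1 |
| unequal | 0 | 4.5 | 8.3 | 6.0 | 4.0 |
| unequal | 0.25 | 5.0 | 10.1 | 7.2 | 5.5 |
| unequal | 0.5 | 2.8 | 9.3 | 6.3 | 4.2 |
| very unequal | 0 | 4.8 | 11.3 | 8.2 | 5.2 |
| very unequal | 0.25 | 4.2 | 10.6 | 7.8 | 5.0 |
| very unequal | 0.5 | 2.8 | 9.3 | 6.9 | 4.2 |

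With an exchangeable working correlation (1,200 runs, SE about 0.8 points), the OPO cluster with a normal reference gave 6.8-12.1%, and with t(13) but no bias correction 5.3-8.9%. With 10 OPOs the normal-reference version reached 9.0-14.4%.

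**OPO indicators with donor-level robust errors.** 4.5-6.0% with 14 OPOs and 4.2-5.8% with 10.

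**The case against.** The strongest reply is that the high error rate belongs to a method the plan does not state. It needs three choices together: OPO clusters, an uncorrected sandwich and a normal reference. Changing only the reference to t(13) brings the independence result to 5.0-8.2%, and adding the Mancl-DeRouen correction brings it to 4.0-5.5%. The plan neither adopts nor excludes either step. This stands. A reader might infer that the planned count test has a false-positive rate of about twice nominal, and the documents do not support that.

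A reader might also take the OPO to be the only sensible cluster. That does not follow either. The stated reason for GEE, flexibility compared with a Poisson model, concerns the count distribution and fits donor-level robust errors at least as well. On that reading false positives are not inflated, and the loss of power on a secondary outcome is modest.

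It can further be said that the amendment log shows an intent to account for site in secondary outcomes, and that OPO indicators are compatible with the current sentence. Both are true. But a GEE has no random effects, so that intent does not tell the analyst what to fit, and the sentence lists only study group and expected organs.

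What remains is that, on either reading with the usual robust errors, the model as written does worse than a version that includes the randomization stratum.

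**Conclusion.** The point holds as an available improvement, and it does not show that the planned test is invalid. The count model leaves out the stratification factor that the section's models for the vasopressor-inotrope score and ejection fraction include.

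- **Donor as cluster:** valid and conservative, with about 2-5% type I error under a common treatment effect and a power loss of roughly 3-9 points for assumed log-scale site SDs of 0.15-0.30. Under the same Poisson assumption the excess variance fraction is mean × s², so for a given SD the loss would be smaller for thoracic organs, whose mean is lower. Thoracic counts were not simulated.
- **OPO as cluster, uncorrected, normal reference:** about 7-12% type I error with about 14 OPOs, conditional on those unstated choices and on the assumed counts, site variation and site sizes.

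The donor-level figure assumes the same effect at every OPO. If effects varied between OPOs around a zero mean (assumed SD 0.2 on the logit scale), donor-level errors rejected in 12-21% of runs over the 10- and 14-site settings. That tests a different null hypothesis and is no evidence against the plan.

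The primary test and the recipient graft-survival analysis are untouched. Priority is low.

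**What to change.** Amend the count-outcome sentence in Statistical methods {20a} so that the model contains study group, expected organs and OPO as a fixed effect, with the donor as the unit for robust standard errors. State the link.

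If the investigators prefer the OPO as cluster, name the working correlation and specify a bias-corrected sandwich (for example Mancl-DeRouen) with a t reference on the number of OPOs minus 1 df, which is 13 for 14 OPOs. Both parts are needed: t(13) without the bias correction still reached 8.2% (independence) and 8.9% (exchangeable).

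The cost is one sentence, fixed before treatment-group data are examined. It needs no extra data and no change in sample size, and standard software fits either version.

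### The interim superiority look at 0.01 is not paid for: the final primary test still uses the full one-sided 0.025, and the halting rule is worded differently in two sections

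*Combined protocol and SAP*

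**What the plan says.** **Interim look.** Section {21b} has the DSMC statistician analyse the data once, at 376 donors with evaluable data. Stopping on the primary outcome is left to discretion: "The trial may be terminated early if, based on the judgement of the DSMC, the interim findings" meet a stated condition. That condition is that they "demonstrate either superiority or clear inferiority of T4 treatment compared to placebo (at a threshold of 0.01"). For recipients it adds: "The trial may also be terminated if there is inferiority of graft outcomes in either group". The DSMC advises the PIs, "who will make final decisions about whether to stop or continue the trial".

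**Final analysis.** Statistical methods {20a} tests the proportion of hearts transplanted "using a one-sided chi-square test at significant level of 0.025", "presenting the absolute and relative differences between the study groups, along with 97.5% one-sided confidence intervals".

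**Sample size.** Sample size {14} asks for 752 donors (376 per group) to detect 35% versus 45%, "assuming 80% power and a one-sided alpha of 0.025", and enrols 800 to allow for losses.

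**Ethics section.** Section {24} refers to the same DSMC-overseen interim. It undertakes to stop the trial if either arm shows a lower number of hearts transplanted or poorer graft results. It gives no threshold and leaves no discretion.

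No section contains a spending function, a group-sequential boundary, a reduced final level, or a statement that an interim crossing would not support a superiority claim.

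**The concern.** The plan gives two opportunities to claim superiority on the primary outcome and counts only the second. The claim rests on an overall one-sided error of 0.025, a level that the version 3.0 amendment deliberately lowered from 0.05. Nothing in the plan holds the error there once the interim look is included, and the final 97.5% confidence bound ignores that look as well.

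The missing sidedness matters because it decides how much alpha the look uses in the superiority direction: 0.01 or 0.005.

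The halting rule raises a second, smaller question. The ethics section offers interim monitoring as one of the protections for recipients, whose consent is waived. A reader of that section is promised a different rule from the one the DSMC is given.

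**Working it through.** **Inputs.** 35% versus 45%, 80% power, one-sided 0.025, 752 needed and 800 enrolled ({14}); 1:1 allocation ({8}); one look at 376 donors with threshold 0.01 ({21b}); final test at one-sided 0.025 ({20a}).

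**1. The plan's own sample size.** With the pooled-variance formula and mean rate 0.40:

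n per group = [1.960·√(2·0.40·0.60) + 0.842·√(0.35·0.65 + 0.45·0.55)]² / 0.10² = 375.6, rounded up to 376, total 752.

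This matches exactly. Power is 80.0% at 376 per group and 82.4% at 400 per group. The calculation is therefore for a single look at 0.025.

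**2. Overall error with both looks.** Under the null, the interim and final statistics Z1 and Z2 are bivariate normal with correlation √t, where t = 376/800 = 0.47 (correlation 0.686) or 376/752 = 0.50 (correlation 0.707). The overall one-sided error is P(Z1 > c1 or Z2 > 1.960).

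| Reading of 0.01 | c1 | Overall error, 800 | Overall error, 752 |
|---|---|---|---|
| One-sided | 2.326 | 0.0307 | 0.0304 |
| Two-sided (0.005 for superiority) | 2.576 | 0.0274 | 0.0273 |

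These are upper values: every crossing is taken to lead to a superiority claim.

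**3. Discretionary stopping.** Suppose only half of the crossings seen at the interim but not at the end led to a claim. At 800 donors the error is then 0.025 + ½(0.0307 − 0.025) = 0.0279, or 0.025 + ½(0.0274 − 0.025) = 0.0262.

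**4. Site stratification.** Randomization is stratified by site, but the primary chi-square is not adjusted for site. That makes it conservative when sites differ. Null trials were simulated (400,000 per scenario, Monte Carlo SE about 0.0003) with 14 equal sites, blocks of 30, a 40% rate, and looks at 376 and 800. The documents give no between-site SD, so it is an assumption shown over a range.

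| Site SD (logit) | Final test alone | With look, 0.01 one-sided | With look, 0.01 two-sided |
|---|---|---|---|
| 0 | 0.0250 | 0.0308 | 0.0275 |
| 0.3 | 0.0244 | 0.0298 | 0.0267 |
| 0.5 | 0.0227 | 0.0278 | 0.0248 |
| 0.8 | 0.0196 | 0.0239 | 0.0213 |

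The look adds 0.004 to 0.006 (one-sided) or 0.002 to 0.003 (two-sided) in every row. The total passes 0.025 up to SD 0.5 on the one-sided reading, and up to SD 0.3 on the two-sided reading.

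**5. Levels that restore 0.025.** Fix the interim boundary and solve for the final level at which the overall error equals 0.025. Power is for 35% versus 45%.

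| Boundary | Interim / final level, 800 | Power, 800 | Interim / final level, 752 | Power, 752 |
|---|---|---|---|---|
| O'Brien-Fleming-type Lan-DeMets | 0.0011 / 0.0246 | 82.3% | 0.0015 / 0.0245 | 79.9% |
| Keep 0.01, one-sided | 0.01 / 0.0187 | 80.1% | 0.01 / 0.0190 | 77.8% |
| Keep 0.01, two-sided | 0.005 / 0.0224 | 81.6% | 0.005 / 0.0226 | 79.2% |

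**6. The two halting rules side by side.**

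| | {21b} | {24} |
|---|---|---|
| Force | Permissive, on DSMC judgement | Unconditional undertaking |
| Hearts criterion | 0.01 | Any lower number, no threshold |
| Graft criterion | Inferiority, no threshold | Any worse outcome, no threshold |
| Who decides | PIs, on DSMC advice | DSMC oversees; decision-maker not named |

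**The case against.** **The excess is small and may not arise.** The stop is discretionary, so the figures in step 2 are ceilings. The plan also expects sites to differ: stratification is justified as "allowing each site to serve as its own control (given heterogeneity in donor management protocols between OPOs"). Under strong heterogeneity the total falls below 0.025. This stands as a limit on size: what is shown is a missing control, not a proven excess. But discretion and unmodelled site variance are not error control, and the look adds error in every scenario examined.

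**The sidedness can be inferred.** Section {20a} says tests will be one-tailed, which favours the one-sided reading and hence the larger inflation. The interim rule looks in both directions, so the question is still open.

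**A graft framework exists elsewhere.** Section {20a} sets a 6% non-inferiority margin at one-sided 0.025, and Adverse event reporting {22} says recipient outcomes will be examined at the interim for non-inferiority. That is fair, but {21b} refers to neither and speaks of inferiority instead.

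**The ethics wording is a loose summary.** This is probably so. Read literally it would stop the trial at almost any numerical difference. Reconciling it is a minor edit, separate from alpha control.

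**The look may already have happened.** Recruitment began on 01 December 2020 and version 3.0 is dated 01 November 2021. At the minimum planned rate of 10 sites × 50 donors = 500 a year, 376 donors take about nine months (376/500 = 0.75 year). Actual enrolment is not given. This limits the choice of remedy but does not remove the need for one.

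**Conclusion.** The concern holds. The plan permits a superiority stop on the primary outcome at 0.01, then tests the same outcome at the full one-sided 0.025 with no allowance for the first look. The overall one-sided error can reach about 0.031 if 0.01 is one-sided, or about 0.027 if two-sided. These ceilings assume that every crossing becomes a claim and that sites share one rate. With marked site differences the total may be below 0.025, but the plan neither relies on that nor controls it.

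The omission itself is certain; the actual inflation is modest and depends on the site variance and on how the DSMC and PIs act. The sample size is correct as a single-look calculation. The mismatch between {21b} and {24} is real but secondary. This should be fixed; it does not undermine the design.

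**What to change.** 1. In {21b}, state whether 0.01 is one- or two-sided and prespecify a boundary that holds overall one-sided 0.025, using the levels in step 5. If the interim has not been carried out, either O'Brien-Fleming-type spending or a retained 0.01 with a stricter final level will do. If it has been carried out at 0.01, only the stricter final level remains.
2. In {20a} and {14}, carry the same final level through to the primary test, the confidence bound and the power statement.
3. In {21b}, state the criterion the DSMC will apply to graft outcomes at the interim and how it relates to the non-inferiority analysis in {20a} and the interim review in {22}.
4. In {24}, replace the separate halting statement with a reference to the single rule in {21b}.

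**Cost.** Protocol and SAP wording, with no added donors. Against a single look at 0.025 (82.4% at 800, 80.0% at 752), O'Brien-Fleming-type spending loses about 0.1 percentage points of power. Keeping a one-sided 0.01 loses about 2.3 points at 800 (82.4 − 80.1) and falls below the 80% target, to 77.8%, if only 752 donors are analysed. Keeping a two-sided 0.01 loses about 0.8 points at either size.
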